## Criteria to enter the 52 weeks Extension Period

Participants who complete the Core Period on study treatment (with Day 29 infusion completed) and meet one of the below criteria at the End of the Core Period (Day 43) will continue in the 52 weeks Extension Period:

- $\geq 50\%$  reduction from the baseline MADRS at the end of Core (Day 43) (participant is a Responder)
- MADRS total score of  $\leq 12$  points at the end of Core (Day 43) (participant is a Remitter)

Any worsening of depressive or suicidal symptoms during the Core Period is not considered a relapse. Participants who do not meet the criteria to continue in the 52 weeks extension will follow an abbreviated extension for 8 weeks and will be categorized as non- responder, or non-remitters, respectively.

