## Response and remission criteria

Response is defined as a  $\geq 50\%$  reduction from the baseline MADRS score at any visit during the study.

Remission is defined as MADRS total score of  $\leq 12$  points at any visit during the study.

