### SoC can be adjusted or modified after the relapse retreatment, as clinically warranted. Extension Follow-up Duration

[figure not shown]
All participants must complete a follow-up period after the End of Core Period visit (Day 43):

- For participants who are neither remitters nor responders at the End of Core Period (Day 43) [Section 3.2](#), the follow up will last 8 weeks and consists of 3 mandatory visits (the 2 weeks Follow-up visit, the 4 weeks Follow up visit and the End of Study visit occurring 8 weeks after Day 43)
- For participants who are responders or remitters at the End of the Core Period (Day 43), and who do not experience any relapse, the Extension Period will last 52 weeks. This will consist of the 2 weeks Follow-up visit, the 4 weeks Follow-up visit, and thereafter Follow-up visits occurring every 4 weeks up to End of Study visit at Week 52
- Participants who are responders or remitters at the End of the Core Period (Day 43), and who relapse during the Extension Period, will receive one course of retreatment with MIJ821.
  - After that course of retreatment:
    - The participant will resume the 4 weekly Follow-up visit schedule (E.g., if the 6 weeks relapse retreatment period occurred from week 19 to 25, the participant will not perform visits week 20 and week 24, and will resume the follow-up at week 28).

- The duration of the follow up will be as per the initial schedule up to Week 52 or clinical worsening, whichever comes first, but they must complete at least 8 weeks follow-up period (see [Section 6.1.4](#)). Signs of clinical worsening may include worsening of depressive mood, need for SoC adjustments, a suicidal attempt, hospitalization for depression or suicidal ideation or behavior. For patient management see [Section 3.4](#), subsection Relapse and Clinical Worsening.
- Participants who are responders or remitters at the End of the Core Period (Day 43), and who relapse during the Extension Period but do not meet the weight requirements of 50-120kg (inclusive), cannot be retreated for the relapse and must be discontinued. The Extension period for these participants should last at least 8 weeks before the discontinuation.

The total duration of the Extension Period is 52 weeks, maximum. Therefore, the last date of confirmed relapse enabling access to the retreatment period is 38 weeks. If a participant relapses on or after that date, the participant must complete the End of Study visit as soon as possible.

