  - Post-dose systolic blood pressure of  $\geq 200$  mmHg and/or the DBP is  $\geq 120$  mmHg confirmed by triplicate reading (at least one value should confirm the blood pressure increase above the defined thresholds).

If discontinuation of study treatment occurs, the investigator should make a reasonable effort to understand and record the primary reason for the participant's premature discontinuation of study treatment.

Participants who discontinue study treatment or who decide they do not wish to participate in the study further should NOT be considered withdrawn from the study UNLESS they withdraw their consent (see [Section 9.1.2](#)). Where possible, they should return for the assessments indicated in the Assessment Schedule. If they fail to return for these assessments for unknown reasons, every effort (e.g. telephone, e-mail, letter) should be made to contact the participant/pre-designated contact as specified in the lost to follow-up section.

If the participant cannot or is unwilling to attend any visit(s), the site staff should maintain regular telephone contact with the participant, or with a person pre-designated by the participant. This telephone contact should preferably be done according to the study visit schedule.

Following study treatment discontinuation (no further infusions planned), participants should be followed for two months beyond the 6 week Core Period (Follow-up Period).

Participants who discontinue study treatment during the Core Period should return at every scheduled visit until the End of the 6 week Core Period. The list of assessments should be kept as planned with the following exceptions: ECG and vital signs to be measured (triplicates required), no PK sampling collection, and all assessments that are repeated several times in one day should be done only once [REDACTED]

[REDACTED] Participants will then enter the two months Follow-up Period.

Participants who discontinue study retreatment during the Extension Period should return for the End of Relapse visit and subsequently enter the two month Follow-up Period.

If an onsite visit is not possible, then telephone visits should be conducted and collected at minimum the following:

- New / concomitant treatments
- Adverse Events / Serious Adverse Events

The investigator must also contact the IRT to register the participant's discontinuation from study treatment.

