2.2.1 Patient disposition

Randomized

Participants are considered randomized if they have been assigned a randomization number.

Completing the Core Treatment

Participants are defined as completing the Core Treatment if they have received 3 scheduled infusions in Core Period. It will be derived from Treatment Disposition Form with “Completed” as participant status. Participant who has infusion interruption or skips the second infusion on Day 15 will not be counted as treatment discontinuation if she/he completes the last infusion on Day 29.

Completing the Core Period

Participants are defined as completing the Core Period if they completed the End of Core Visit (Day 43). Participants who discontinue core treatment are encouraged to continue the scheduled visit as indicated in the Assessment Schedule (Protocol Table 8-1).

Eligible for Retreatment in Extension Period

Participants who complete the Core Period on study treatment (with Day 29 infusion completed), and are classified as responders or remitters at the end of Core Period, will be eligible for retreatment with MIJ821 once observe relapse during the Extension Period.

Completing the Retreatment in Extension Period

Participants who are eligible for retreatment and have received 3 scheduled infusions in Extension Period, will be considered as completing the retreatment. It will be derived from Retreatment Disposition Form with “Completed” as participant status. Participant who has infusion interruption or skip the second infusion on Day 15 (Retreatment Period) will not be counted as treatment discontinuation if she/he completes the last infusion on Day 29 (Retreatment Period).

Completing the Extension Period

Participants who are classified as responders or remitters at the end of Core Period will be deemed as completing the Extension Period if they have been observed for 52 weeks in Extension Period or up to clinical worsening after re-treatment, whichever comes first. Participants who are neither responders nor remitters at end of Core Period will be deemed as completing the Extension Period if they have completed the minimum 8 weeks’ safety follow-up in Extension Period.

Participant disposition will be displayed by randomized treatment and overall, in terms of:

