2.5.1 Secondary endpoints

To assess the effect of MIJ821 on sustained response and remission, following secondary efficacy endpoints will be evaluated:

- Proportion of participants meeting response criteria ($\geq 50\%$ reduction from baseline in MADRS total score) over time in the Core Period.
 - Participants who do not meet the criterion or discontinue Core Period prior to the time point due to any reason or with missing score (baseline and/or post baseline) will not be considered as "a responder" at that timepoint.
- Proportion of participants meeting criteria for sustained response ($\geq 50\%$ reduction from baseline in MADRS total score sustained for a period of at least four weeks) in the Core Period

- The sustained response ideally requires all scheduled assessments over four weeks achieving 50% reduction from baseline. However, if there is one or more missing assessment(s) between two responses, the response will be assumed to be sustained over missing assessment(s), unless other specified. For example, one participant observed a response at Day 1 4 hours, Day 29 -2 hours, however missed the assessment at 24 hours, Day 8, Day 15 and Day 22, this participant is still considered as meeting the sustained response. The missing due to study discontinuation will not be imputed. Participants who do not meet the criterion will not be considered as “a responder” at the timepoint.
- Proportion of participants meeting remission criteria (MADRS total score of ≤ 12) over time in Core Period
 - Participants who do not meet the criterion or discontinue prior to the time point due to any reason or with missing score (either at baseline or post baseline) will not be considered as “a remitter” at that timepoint.
- Proportion of participants meeting criteria for sustained remission (MADRS total score of ≤ 12 sustained for a period of at least four weeks) in the Core Period
 - The rule for sustained remission is the similar with sustained response. Participants who do not meet the criterion will not be considered as “a remitter” at the timepoint.
- Proportion of participants meeting criteria for relapse over fixed period in the Extension Period
 - The definition and criteria of relapse could be referred to protocol section 3.4. The relapse will be evaluated by investigator and reported in the CRF form “Relapse and re-treatment criteria”. Participants without relapse reported will not be counted.

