2.5.2 Statistical hypothesis, model, and method of analysis

Analysis of above secondary efficacy endpoints will be based on FAS (Core Period) or RTS (Retreatment Period), except the following endpoints:

- Proportion of participants meeting criteria for relapse over fixed period in the Extension Period will be based on ENS
- Proportion of relapsing participants meeting response criteria or remission criteria after the first infusion of MIJ821 retreatment in the Extension Period will be based on RTS

No hypothesis will be tested for the secondary efficacy endpoints.

Frequency tables (count and proportion) will be provided for these endpoints by analysis visit after imputation for missing values. Details on missing data handling are described in [Section 2.5.1](#). Bar chart will be plotted by treatment arm and analysis visit.

The proportion of participants meeting criteria for relapse over 1 month, 2 months, 3 months, 6 months 9 months and 12 months in Extension Period will be plotted for each treatment arm based on ENS for responders/remitters at EoC visit. In addition for responders/remitters, the time to first relapse will be analyzed by kaplan-meier (KM) method and display in KM plots. The median time to first relapse will be summarized with 90% CI.

If data warranted, the treatment differences of each MIJ821 dose versus Placebo will be analyzed separately, using a repeated logistic regression model, for following endpoints:

- Proportion of participants meeting response criteria ($\geq 50\%$ reduction from baseline in MADRS total score) over time in the Core Period.
- Proportion of participants meeting criteria for sustained response ($\geq 50\%$ reduction from baseline in MADRS total score sustained for a period of at least four weeks) in the Core Period
- Proportion of participants meeting remission criteria (MADRS total score of ≤ 12) over time in Core Period
- Proportion of participants meeting criteria for sustained remission (MADRS total score of ≤ 12 sustained for a period of at least four weeks) in the Core Period

For response rate and remission rate per visit, the repeated logistic regression model will be established with the fixed, categorical effects of treatment (6 dose arms and 1 placebo arm), time, treatment*time interaction, region, the fixed continuous baseline MADRS score, and baseline score*time interaction. [REDACTED]

[REDACTED]

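### Day 43 responders who have stopped study treatment have conflicting labels and follow-up lengths, so the relapse cohort is unsettled and crude 3 to 12 month relapse proportions can be biased downward

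*Protocol*

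**What the plan says.** **Entry to the 52-week Extension (Protocol 3.2).** Two conditions apply. The first is on-treatment completion: "Participants who complete the Core Period on study treatment (with Day 29 infusion completed"). The second is response or remission at Day 43. Those who do not meet the criteria "will follow an abbreviated extension for 8 weeks and will be categorized as non- responder, or non-remitters, respectively".

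**Definition of response (Protocol 3.2).** The definition rests on the score alone, a fall of at least 50%: "reduction from the baseline MADRS score at any visit during the study". Remission is likewise a score threshold.

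**After stopping treatment (Protocol 9.1.1).** Participants who stop during Core are asked to attend the remaining Core visits, so a Day 43 MADRS can exist. Then: "Participants will then enter the two months Follow-up Period".

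**Extension follow-up (Protocol 3.3).** For those who are responders or remitters at Day 43 and "who do not experience any relapse, the Extension Period will last 52 weeks". No on-treatment condition is attached.

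**Completing the Extension (SAP 2.2.1).** "Participants who are classified as responders or remitters at the end of Core Period will be deemed as completing the Extension Period" once observed for 52 weeks, or to clinical worsening after retreatment. Again there is no on-treatment condition.

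**Response endpoint (SAP 2.5.1).** Those not counted as responders are: "Participants who do not meet the criterion or discontinue Core Period prior to the time point due to any reason or with missing score". Stopping study treatment is not in that list. For relapse, the same section does not count anyone without a reported relapse.

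**Relapse analysis (SAP 2.5.2).** The proportions over 1, 2, 3, 6, 9 and 12 months "will be plotted for each treatment arm based on ENS for responders/remitters at EoC visit". A Kaplan-Meier analysis of time to first relapse is also planned for responders/remitters, with no censoring rule stated.

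**The concern.** Take a participant who stops infusions, for example after an adverse event, keeps attending, and has halved the baseline MADRS by Day 43. The extension-entry text calls this person a non-responder with 8 weeks of follow-up. The score definition calls the same person a responder, and the follow-up and completion texts attach 52 weeks to that status.

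Three outputs depend on how this is settled:

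- the count of responders/remitters at End of Core in the disposition table (SAP 2.2.1);
- who counts as having completed the Extension;
- who belongs to the relapse cohort, and for how long they are observed.

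The third matters most. If such participants enter the cohort by score but leave at 8 weeks, the fixed-period proportions treat their unobserved months as relapse-free. Arms with more stopping would then look more durable. Time to relapse is among the main analyses of the unblinded interim (SAP 2.1), and that interim is where the dose and regimen are chosen (SAP 2.11).

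**Working it through.** **1. One participant, each rule in turn.** The participant stopped treatment, attended throughout, and is a MADRS responder at Day 43.

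| Place | Label | Follow-up |
|---|---|---|
| Protocol 3.2, extension entry | non-responder / non-remitter | 8 weeks |
| Protocol 3.2, response definition | responder | not addressed |
| Protocol 3.3, follow-up duration | responder | 52 weeks |
| Protocol 9.1.1 | not addressed | two months |
| SAP 2.2.1, Extension completion | responder, if classified by score | 52 weeks to count as complete |
| SAP 2.5.1, response endpoint | responder | not addressed |
| SAP 2.5.2, relapse cohort | included, if classified by score | not addressed |

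A participant followed exactly as Protocol 3.2 and 9.1.1 direct would therefore be reported under SAP 2.2.1 as not completing the Extension, if classified by score.

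**2. Inputs for size.** The documents give no rate of treatment stopping, Day 43 response or relapse, so there is no planned figure to reproduce for this point. Only the arm size is taken from the plan: 6 × 30 + 15 = 195 randomized, which matches. The remaining inputs are assumptions:

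- 12-month relapse of 40% with constant hazard;
- a share d of Day 43 responders with 8 weeks of follow-up only, d = 5%, 10% or 20%;
- 50% response at Day 43.

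**3. Crude 12-month relapse proportion.** Relapse by 8 weeks = 1 − 0.6^(8/52) = 0.076. These early relapses are counted at every later horizon.

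Crude proportion = (1 − d) × 0.40 + d × 0.076:

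- d = 5%: 0.380 + 0.004 = 38.4%
- d = 10%: 0.360 + 0.008 = 36.8%
- d = 20%: 0.320 + 0.015 = 33.5%

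Two arms with the same true risk but 5% and 20% on short follow-up would differ by 38.4 − 33.5 = 4.9 points.

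**4. Sensitivity at 10%.** Suppose 10% of participants stop treatment but still have a Day 43 score. If they respond half as often as the others (25% against 50%), the short-follow-up share of responders falls to 0.025/(0.45 + 0.025) = 5.3%, and the crude figure is 38.3%. If they respond equally often but relapse more (60% at 12 months), full follow-up would give 0.9 × 0.40 + 0.1 × 0.60 = 42.0%. The crude figure would be 0.9 × 0.40 + 0.1 × (1 − 0.4^(8/52)) = 37.3%.

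**5. Against sampling error.** With 30 × 0.5 = 15 responders per arm, SE = √(0.4 × 0.6/15) = 12.6 points. The shifts of 1.6, 3.2 and 6.5 points are all smaller.

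**6. Disposition count.** At 10% stopping with 25% to 50% response among those who stop, the label moves 30 × 0.10 × 0.25 = 0.8 to 30 × 0.10 × 0.50 = 1.5 participants per 30-participant arm, or 2.5 to 5 points.

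**The case against.** **The protocol can be read consistently.** Protocol 3.3 refers back to 3.2 for who is classified as a responder or remitter. If that word always carries the on-treatment condition, this participant gets 8 weeks everywhere and is outside the relapse cohort. This is a fair reading of the protocol alone. It does not carry into the SAP, where sections 1.1 and 2.2.1 list on-treatment completion and responder classification as two separate conditions for retreatment.

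**Kaplan-Meier is already planned.** This stands, and it limits the damage to time to relapse. But no censoring rule is stated, and nothing says that the 1 to 12 month proportions come from that analysis.

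**The endpoint is secondary and untested, and the effect is small.** This also stands. Lack of effect is itself a reason to stop treatment (Protocol 9.1.1), so stoppers may respond less often and the affected share may be lower than d.

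**Stronger readings that the documents do not support:**

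- A reader might infer that the Day 43 response and remission rates depend on which rule is used. They do not. SAP 2.5.1 fixes both by score, and no analysis text brings in the extension-entry label. The remission bullet says only that the participant discontinues, without naming the Core Period. It sits in the same list of Core endpoints, so a different rule is unlikely to be meant.
- A reader might infer that participants followed for 8 weeks can never count as relapsed at later horizons. A relapse within those 8 weeks counts at all of them.
- A reader might infer that higher doses will be flattered. The documents report dose-related adverse events (amnesia 9.5% at 0.16 mg/kg and 42.1% at 0.32 mg/kg in the proof-of-concept study, the latter dose not used here), but no rates of treatment stopping by dose.

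**Conclusion.** The conflict is real in the current text of both documents, but narrow. It concerns participants who stop treatment, stay in Core and respond or remit by Day 43. It affects the End of Core disposition count, the Extension completion count and the relapse cohort. It leaves the 24-hour primary analysis and the response and remission endpoints untouched.

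If the SAP is followed as written and these participants are classified by score but followed for 8 weeks, the crude relapse proportions at 3, 6, 9 and 12 months are biased downward. At 12 months the bias is about 2 to 6 points for a 5% to 20% short-follow-up share. That size rests entirely on the assumed 40% relapse, constant hazard and stopping shares. It lies within the sampling error of a single arm, so it would rarely decide a dose choice by itself. It is still a systematic error that wording can remove.

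**What to change.** **SAP 2.5.2:** adopt one of two options.

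- Define the relapse cohort as participants with the Day 29 infusion completed who are responders or remitters at Day 43.
- Keep all Day 43 responders/remitters, and read the 1 to 12 month proportions from the planned Kaplan-Meier analysis, censoring at the last Extension visit. This assumes that censoring is unrelated to relapse risk, which should be stated.

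The same paragraph should say how the chosen cohort relates to the all-randomized denominator named for this endpoint in Protocol Table 2-1 and SAP Table 1-1.

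**SAP 2.5.1 and 2.2.1:** state that the label in the extension-entry text of Protocol 3.2 does not govern the response and remission endpoints, and say which definition the disposition count uses.

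**Protocol 3.2, 3.3 and 9.1.1 with SAP 2.2.1:** the sponsor must reconcile follow-up length and the responder label for participants who are off treatment. The label also determines who may change standard of care in the Extension (Protocol 3.3, Standard of Care, and 6.2.1), so it should not simply be deleted. Which rule is right is for the sponsor.

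**Cost:** for the analysis points, SAP wording only, with no new patients or data. The protocol reconciliation needs a clarification that checks the standard-of-care text at the same time.

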### 3.3 Double-blind Extension Period

After completing the double-blind Core Period, all participants will enter the Extension Period for a minimum of 8 weeks and a maximum of 52 weeks.

Those participants who are not responders and not remitters at the end of the Core Period (see in this section, subsection Extension Follow-up duration for more details ), will be observed in an abbreviated Extension Period lasting 8 weeks only to obtain safety data and evaluate withdrawal and rebound effects of MIJ821. Because those participants did not respond to the treatment as defined in [Section 3.2](#) in the first instance, no retreatment will be provided in case of relapse. Those participants are allowed to adjust their SoC in their 8 weeks Extension Period, as necessary.

## Study treatment

Participants who are classified as responders or remitters at the end of the Core Period (see [Section 3.2](#) for more details), will be eligible to one retreatment course in case of a relapse

in the Extension Period, and should be observed for up to 52 weeks or clinical worsening after retreatment, whichever comes first (see in this section, subsection Extension Follow up Duration, and [Section 3.4](#)).

In the event of relapse (see [Section 3.4](#) retreatment in case of relapse), participants will receive study treatment (called retreatment), as in the Core Period, in a blinded manner. All participants will be pre-randomized to relapse retreatment on Day 1 in the Core Period as described below:

- Participants who were receiving MIJ821 in the Core Period will be assigned to the same dose and regimen for the retreatment in case of relapse (if any in the Extension Period)
- Participants who were randomized to placebo in the Core Period will be assigned to one of the active treatment arms in the Extension Period (see [Section 6.3.2](#))

After the dose and dose regimen for Phase 3 have been selected after the interim analysis, participants who relapse will receive the selected Phase 3 dose and regimen in a dose-blinded manner for the retreatment in case of relapse. Patients who have already started retreatment for the relapse will continue on the originally assigned dose.

